11.2.1 Dose Modification Guidelines

Patients will be monitored continuously for AEs while on study. Treatment modifications (e.g., dose delay) will be based on specific laboratory and AE criteria. Guidelines for dose modifications due to hematological and non-hematological AEs are provided in [Tables 11.2-1](#) and [11.2-2](#), respectively. The dose levels for CB-839 dose reduction are provided in [Table 11.2-3](#). For everolimus dose reduction levels, the most up-to-date everolimus Package Insert applicable to the site location should be consulted and followed.

These dose modification guidelines provided in [Tables 11.2-1](#) and [11.2-2](#) are based on the Package Insert for everolimus (dated September 2017) and the clinical experience with CB-839 and the combination to date. These guidelines are intended primarily for toxicities that are not easily managed with routine supportive care. Because everolimus prescribing information may change over time, the most up-to-date everolimus Package Insert applicable to the site location should be consulted and followed.

Table 11.2-1: Dose Modifications Guidelines for Hematologic Toxicity

Toxicity Grade (CTCAE v4)	Management of toxicity	CB-839 or Placebo	Everolimus
Hematologic: Grade 3/4 (other than those highlighted below)	Supportive care, as necessary	Hold and resume at the same dose level upon resolution to \leq Grade 1 or baseline	Hold everolimus and resume at the same dose level upon resolution to \leq Grade 1 or baseline. If toxicity recurs at Grade 3, hold and restart at the next lower dose
Grade 3/4 neutropenia or thrombocytopenia	Supportive care, as necessary	Hold and resume at the same dose level upon resolution to \leq Grade 1 or baseline	Hold everolimus and resume at one dose level lower upon resolution to \leq Grade 1 or baseline

Table 11.2-2: Dose Modifications Guidelines for Non-Hematologic Toxicity

Toxicity Grade (CTCAE v4)	Management of toxicity	CB-839 or Placebo	Everolimus
Non-hematologic clinically significant: (other than those highlighted below) Grade 2	Initiate appropriate medical therapy and monitor	If symptom not tolerable, hold and resume at the same dose level upon recovery to \leq Grade 1 or baseline. If toxicity recurs, hold and restart at next lower dose.	If symptom not tolerable hold everolimus and resume at same or next lower dose level upon recovery to \leq Grade 1. If toxicity recurs at Grade 2, hold and restart at next lower dose.
Non-hematologic clinically significant: (other than those highlighted below) Grade 3	Initiate appropriate medical therapy and monitor	Hold and resume at the same dose level or the next lower dose level upon recovery to \leq Grade 1 or baseline.	Hold everolimus and resume at the next lower dose level upon recovery to \leq Grade 1. If toxicity recurs at Grade 3, consider discontinuation.
Non-hematologic clinically significant: (other than those highlighted below) Grade 4	Initiate appropriate medical therapy and monitor	Permanently discontinue	Permanently discontinue everolimus
Non-infectious pneumonitis Grade 1	Monitor by CT at least every 3 cycles.	Continue	Continue everolimus.
Grade 2	Rule out infection and consider treatment with corticosteroid until symptoms improve to \leq Grade 1.	Hold and resume at the same dose level upon recovery to \leq Grade 1 or baseline.	Hold everolimus and resume at the next lower dose level upon recovery to \leq Grade 1 or baseline.

Toxicity Grade (CTCAE v4)	Management of toxicity	CB-839 or Placebo	Everolimus
Grade 3	Rule out infection and consider treatment with corticosteroid until symptoms improve to \leq Grade 1.	Hold and resume at the same dose level upon recovery to \leq Grade 1 or baseline.	Hold everolimus and resume at the next lower dose level upon recovery to \leq Grade 1 or baseline. If toxicity recurs at Grade 3, then consider discontinuation.
Grade 4	Rule out infection and consider treatment with corticosteroid until symptoms improve to \leq Grade 1.	Hold and resume at the same dose level upon recovery to \leq Grade 1 or baseline.	Permanently discontinue everolimus
Stomatitis Grade 2	Manage with topical analgesic mouth treatments as per everolimus Package Insert and local practice.	Consider holding. If held resume at the same dose upon recovery to \leq Grade 1	Hold everolimus and resume at the same dose level upon recovery to \leq Grade 1. If toxicity recurs at Grade 2 hold and resume at next lower dose level upon recovery to Grade 1
Stomatitis Grade 3	Manage with topical analgesic mouth treatments as per everolimus Package Insert and local practice.	Hold and resume at the same dose or the next lower dose upon recovery to \leq Grade 1	Hold everolimus and resume at the next lower dose upon recovery to \leq Grade 1
Stomatitis Grade 4	Manage with topical analgesic mouth treatments as per everolimus Package Insert and local practice.	Hold and resume at the next lower dose upon recovery to \leq Grade 1	Permanently discontinue everolimus
Metabolic events (e.g. hyperglycemia, dyslipidemia) Grade 1-2	Manage with appropriate medical therapy.	Continue	Continue
Metabolic events (e.g. hyperglycemia, dyslipidemia) Grade 3	Manage with appropriate medical therapy	Hold and resume at the same dose level or one dose level lower upon recovery to \leq Grade 1 or baseline	Hold everolimus and resume at next lower dose level upon recovery to \leq Grade 1 or baseline.
Metabolic events (e.g. hyperglycemia, dyslipidemia) Grade 4	Manage with appropriate medical therapy	Hold and resume at one dose level lower upon recovery to \leq Grade 1 or baseline	Permanently discontinue everolimus

Table 11.2-3: Dose Reductions for CB-839 (or Placebo)

Dose Reductions of CB-839 or Placebo		
Dose Level	CB-839 Dose	Number of Tablets CB-839 or Placebo
Starting dose	800 mg BID	4
First dose reduction	600 mg BID	3
Second dose reduction	400 mg BID	2
Third dose reduction	Discontinue CB-839 or Placebo	0

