ANAEMIA	13 (68.4)	5 (26.3)
DECREASED APPETITE	9 (47.4)	0
BLOOD CREATININE INCREASED	7 (36.8)	0
HYPERGLYCAEMIA	7 (36.8)	2 (10.5)*
COUGH	6 (31.6)	0
NAUSEA	6 (31.6)	0
DIARRHOEA	5 (26.3)	1 (5.3)
HEADACHE	5 (26.3)	1 (5.3)
PROTEINURIA	5 (26.3)	0
VOMITING	5 (26.3)	0
ASPARTATE AMINOTRANSFERASE INCREASED	4 (21.1)	0
FATIGUE	4 (21.1)	2 (10.5)
STOMATITIS	4 (21.1)	0
ABDOMINAL PAIN	3 (15.8)	1 (5.3)
ALANINE AMINOTRANSFERASE INCREASED	3 (15.8)	0
CHILLS	3 (15.8)	0
DERMATITIS ACNEIFORM	3 (15.8)	0
DYSGEUSIA	3 (15.8)	0
DYSPNOEA	3 (15.8)	0
HYPOMAGNESAEMIA	3 (15.8)	0
HYPOPHOSPHATAEMIA	3 (15.8)	1 (5.3)
INSOMNIA	3 (15.8)	0
MUCOSAL INFLAMMATION	3 (15.8)	0
MYALGIA	3 (15.8)	1 (5.3)
PAIN	3 (15.8)	1 (5.3)
PLATELET COUNT DECREASED	3 (15.8)	0
PYREXIA	3 (15.8)	0
THROMBOCYTOPENIA	3 (15.8)	0
WEIGHT DECREASED	3 (15.8)	0

*preexisting diabetes

Treatment-related adverse events that were Grade 3 were few in number and there have been no Grade 4 events (Table 9.5-4). One event of Grade 3 rash occurred at the 400 mg BID dose level, which was considered a dose limiting toxicity (DLT). The rash was considered related to everolimus and resolved upon a dose reduction of everolimus (CB-839 continued at full dose). No additional DLTs have been reported in subsequent patients treated at 400, 600 or 800 mg BID and a maximum tolerated dose has not been identified.

Table 9.5-4: Treatment-Related Adverse Events in ≥ 3 Patients Treated with CB-839 + Everolimus on Study CX-839-001

CB-839 + Everolimus (N=19): Treatment-related TEAEs*		
MedDRA Preferred Term	Number (%) of patients	
	All Events	\geq Grade 3[^]
Patients with Any Treatment-related TEAE in CBE cohort	19 (100)	9 (47.4)
DECREASED APPETITE	7 (36.8)	0
ANAEMIA	5 (26.3)	1 (5.3)
DIARRHOEA	5 (26.3)	0
HYPERGLYCAEMIA	5 (26.3)	2 (10.5)
PROTEINURIA	5 (26.3)	0
ASPARTATE AMINOTRANSFERASE INCREASED	4 (21.1)	0
BLOOD CREATININE INCREASED	4 (21.1)	0
FATIGUE	4 (21.1)	2 (10.5)
NAUSEA	4 (21.1)	0
STOMATITIS	4 (21.1)	0
ALANINE AMINOTRANSFERASE INCREASED	3 (15.8)	0
DERMATITIS ACNEIFORM	3 (15.8)	0
DYSGEUSIA	3 (15.8)	0
MUCOSAL INFLAMMATION	3 (15.8)	0
MYALGIA	3 (15.8)	0
THROMBOCYTOPENIA	3 (15.8)	0
VOMITING	3 (15.8)	0

[^]no Grade 4 or Grade 5 events

*considered to be at least possibly related to either CB-839 or everolimus

Please refer to the most recent CB-839 Investigator's Brochure for additional safety information from the Phase 1 studies.

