11.1.2 Everolimus

Adverse events most frequently observed with everolimus are rash, stomatitis/oral mucositis, fatigue, headache, anorexia, nausea, vomiting, diarrhea, and infections (see everolimus Package Insert). Overall, the most frequently observed laboratory abnormalities include neutropenia, thrombocytopenia, hypercholesterolemia, and/or hypertriglyceridemia. The majority of these AEs have been of mild to moderate severity (CTCAE Grade 1-2). Everolimus has been associated with a low incidence of severe and potentially lethal AEs, including non-infectious pneumonitis, infections, and renal failure (see Warnings and Precautions in the Package Insert). Everolimus dosing and toxicity should be managed according to the Package Insert and local institutional practice.

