11.2.2 Resumption of Study Treatment

For everolimus and CB-839 (or placebo), treatment may be delayed for up to 6 weeks from the last dose. Delays longer than 6 weeks are allowed only in cases where the delay was due to a non-drug related cause. Prior to re-initiating treatment in a patient with a dosing interruption lasting > 4 weeks, the Medical Monitor must be consulted. Treatment compliance will be monitored by drug accountability as well as the patient's medical record and eCRF.

Upon withholding study drugs for adverse events, the study drugs may be restarted when the AE has returned to \leq Grade 1 or baseline. In cases in which a particular toxicity is clearly related to only one of CB-839 or everolimus, the study drug that is not involved in causing the AE may be restarted prior to a return to \leq Grade 1 or baseline. If CB-839 (or placebo) is restarted after permanent discontinuation of everolimus, CB-839 or placebo should be permanently discontinued for a \geq Grade 3 recurrence of the AE that resulted in everolimus discontinuation.

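### Two dose-modification passages are internally inconsistent: the Grade 3/4 recurrence wording in Table 11.2-1, and the general Grade 3 and 4 rows of Table 11.2-2 against the early-restart exception in 11.2.2

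*Protocol*

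**What the plan says.** **Table 11.2-1 (protocol 11.2.1), first row.** The row is for Grade 3/4 hematologic toxicity other than neutropenia and thrombocytopenia, which have their own row. Everolimus is held and resumed at the same level on recovery. One recurrence instruction follows: "If toxicity recurs at Grade 3, hold and restart at the next lower dose".

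**Table 11.2-2 (protocol 11.2.1), general non-hematologic rows.** These cover clinically significant events without a row of their own.
- At Grade 3 the everolimus cell reads "Hold everolimus and resume at the next lower dose level upon recovery to" Grade 1 or below.
- At Grade 4 it reads "Permanently discontinue everolimus", and CB-839 or placebo is also stopped permanently.
- Neither row asks which drug caused the event.

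**Section 11.2.2.** The general rule is restart on recovery to Grade 1 or baseline. An exception follows for an event that can plainly be put down to one of the two drugs and not the other. It says that "the study drug that is not involved in causing the AE may be restarted prior to a return to" that level. It states no restart dose and does not refer to the tables.

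**Section 11.1.2.** "Everolimus dosing and toxicity should be managed according to the Package Insert and local institutional practice".

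Section 11.2.1 calls the tables guidelines, says they are based on the September 2017 everolimus insert, and tells sites to follow the current insert.

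**The concern.** A dose-modification table should give one answer for one event. Here two kinds of event can get two.

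The first is a recurrent hematologic event. The heading of the first row of Table 11.2-1 promises a rule for Grades 3 and 4, but the recurrence wording delivers one for Grade 3 only. The more severe recurrence then falls back to the more lenient instruction.

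The second is a general Grade 3 or 4 non-hematologic event clearly due to one drug. One site can follow the table row and another can use 11.2.2. They would give different everolimus dosing for the same event, and both could claim to be following the protocol.

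At stake is patient safety after serious toxicity, and uniform handling across sites of a drug given in both arms.

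**Working it through.** No planned figure rests on these passages, so the check is mainly a comparison of texts.

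**Part 1: Table 11.2-1, first row, everolimus**

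| Event | What the row yields, read literally |
|---|---|
| First Grade 3 or Grade 4 | Hold, resume at same level on recovery |
| Recurrence at Grade 3 | Hold, restart one level lower |
| Recurrence at Grade 4 | No recurrence rule; the base instruction (same level) applies |

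Anemia is the obvious event for this row, since it is not in the neutropenia/thrombocytopenia row. In the Phase 1 combination cohort, Grade 3 or higher anemia occurred in 5 of 19 patients (26.3%, Table 9.5-3). It was judged treatment-related in 1 of 19 (5.3%, Table 9.5-4). The documents do not say how many such events recurred, or at what grade, so the number of patients who would meet the gap cannot be estimated.

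**Part 2: Table 11.2-2 general rows against 11.2.2, everolimus**

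| Event | Table 11.2-2 | Section 11.2.2 | Result |
|---|---|---|---|
| Grade 3, due to everolimus or both drugs | Hold to Grade 1 or below, then one level lower | Exception does not release everolimus | No conflict |
| Grade 3, clearly due to CB-839 alone | Hold to Grade 1 or below, then one level lower | May restart earlier, level not stated | Timing differs, dose unresolved |
| Grade 4, clearly due to CB-839 alone | Permanently discontinue | Read literally, may restart | Nothing says which governs |

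The Grade 3 case is realistic. Section 11.1.1 names liver function test elevations as the most frequent Grade 3/4 events related to CB-839 monotherapy. Table 11.2-2 has no liver row, so these fall in the general rows.

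The CB-839/placebo cells of these rows have no cause condition either. An event clearly due to everolimus therefore raises the mirror question for CB-839. The count below covers only the everolimus side.

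**Size of part 2 (illustration)**

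Inputs: 3 of 88 patients on twice-daily monotherapy had a CB-839-related event of Grade 3 or higher, none of them Grade 4 or 5 (Table 9.5-2). The planned CBE arm is 42 patients (protocol 14.5).
- Rate: 3/88 = 3.4%; Clopper-Pearson 95% CI 0.7% to 9.6%.
- Expected CBE patients: 42 × 3/88 = 1.4.
- Range: 42 × 0.0071 = 0.3 to 42 × 0.0964 = 4.0.

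This assumes that the monotherapy rate carries over to the combination.

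**The case against.** **Section 11.2.2 is an exception, not a rival rule.** It is narrow and permissive and applies only when one drug is clearly responsible. It speaks of drugs that were withheld, so it may never have been meant to undo permanent discontinuation. Its last sentence deals with CB-839 restarted after everolimus has been stopped for good, which the Grade 4 pneumonitis, stomatitis and metabolic rows can produce. That suggests it was written to be read with the tables. This is a fair reading and it narrows the point. It still leaves the restart level unstated, and no sentence confirms the reading.

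**The tables do not work by grade alone.** A reader might infer that they do. They do not: rows depend on toxicity type as well as grade, the two drug columns differ, and some rows turn on recurrence, investigator choice or tolerability. The general Grade 2 everolimus cell, for example, says "If symptom not tolerable hold everolimus and resume at same or next lower dose level upon recovery to" Grade 1 or below. The supportable statement is that the general Grade 3 and 4 rows take no account of cause.

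**Section 11.1.2 is not a further competing rule.** Section 11.2.1 already ties the tables to the current insert, and the stomatitis rows themselves cite the insert and local practice. Only the rank of local institutional practice against the tables is open.

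**The Phase 1 rash shows the reverse case.** "The rash was considered related to everolimus and resolved upon a dose reduction of everolimus (CB-839 continued at full dose"). This shows that an event was managed by cause before, not that everolimus was reduced for CB-839 toxicity.

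**The Table 11.2-1 wording may be a slip** for Grade 3 or worse, and the current insert may fill the gap. Either is possible. The insert is not part of these documents, and the row as printed does not say so.

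**Conclusion.** Both inconsistencies stand as defects of wording and should be corrected. In Table 11.2-1 the row heading and the recurrence wording cover different grades, and the literal result is less strict for the worse event. In Table 11.2-2 the general Grade 3 row and 11.2.2 give different restart timing for everolimus after an event clearly due to CB-839. The restart level is missing, and nothing says whether the exception reaches the Grade 4 row. The unranked reference to local practice in 11.1.2 would be only a missing detail on its own.

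The grounds are patient safety and consistent dosing after Grade 3/4 toxicity. For everolimus, the attribution conflict probably affects few patients: about 1.4 of 42 in CBE (0.3 to 4.0) if the monotherapy rate applies. Blinding narrows it further, because CB-839 is harder to name as the clear cause when the tablets may be placebo. The frequency of Grade 4 hematologic recurrence is unknown.

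Two stronger readings are tempting, and the documents support neither.
- A reader might scale up the 9 of 19 Phase 1 combination patients with a treatment-related Grade 3 or higher event (Table 9.5-4). That count takes events related to either drug. It includes everolimus-caused events, for which 11.2.2 does not release everolimus, and anemia and hyperglycemia, which fall outside the general rows.
- A reader might infer that the PFS hazard ratio is compromised. The objective compares the two regimens, patients are analyzed as randomized, and the SAP (8.6.1) summarizes dose intensity by arm, so a difference in exposure would be visible. No figure in the documents points to a material shift.

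**What to change.** Amend the protocol wording as follows.

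1. **Table 11.2-1, first row:** make the heading and the everolimus recurrence wording cover the same grades, so that a Grade 4 recurrence has an explicit instruction.
2. **Table 11.2-2, general Grade 3 and 4 rows, and 11.2.2:** cross-reference them. State which governs when an event is clearly due to one drug, at what level the other drug restarts, and whether the exception applies where the row requires permanent discontinuation. Cover both drug columns.
3. **Section 11.1.2:** state how local institutional practice ranks against the tables.

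The sponsor decides the clinical content of each rule; the request is only that the passages agree and give all sites one answer. The cost is text in an amendment and notice to sites, with no added procedures, visits or patients.

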11.2.2 Resumption of Study Treatment

For everolimus and CB-839 (or placebo), treatment may be delayed for up to 6 weeks from the last dose. Delays longer than 6 weeks are allowed only in cases where the delay was due to a non-drug related cause. Prior to re-initiating treatment in a patient with a dosing interruption lasting > 4 weeks, the Medical Monitor must be consulted. Treatment compliance will be monitored by drug accountability as well as the patient's medical record and eCRF.

Upon withholding study drugs for adverse events, the study drugs may be restarted when the AE has returned to \leq Grade 1 or baseline. In cases in which a particular toxicity is clearly related to only one of CB-839 or everolimus, the study drug that is not involved in causing the AE may be restarted prior to a return to \leq Grade 1 or baseline. If CB-839 (or placebo) is restarted after permanent discontinuation of everolimus, CB-839 or placebo should be permanently discontinued for a \geq Grade 3 recurrence of the AE that resulted in everolimus discontinuation.

11.3 Missed Doses

Missed doses of CB-839 or everolimus should be skipped. If a patient forgets to take a dose of CB-839 or everolimus and he/she is outside of the allotted window period (\pm 6 hr), he/she should be instructed to skip that dose and NOT to take extra study drug at their next administration.

11.4 Discontinuation of Treatment and Withdrawal of Patients

The reasons a patient may discontinue or be withdrawn from the study include, but are not limited to, disease progression, adverse events, patient request, withdrawal of consent, investigator decision, protocol violation, patient noncompliance, and study termination by the Sponsor.

In unusual cases where the investigator believes that a patient is clearly experiencing clinical benefit despite radiographic progression per RECIST 1.1, and that the potential benefit of continuing study treatment outweighs the potential risks, extension of study treatment beyond PD may be considered in consultation with the medical monitor.

When a patient discontinues or is withdrawn, the Investigator will notify the Sponsor (or designee) and should perform all End of Treatment and follow up procedures as indicated in the schedule of study assessments ([Attachment 1](#)) after discontinuation of study drug. *Note that patients who discontinue study treatment for reasons other than progressive disease or death should be followed by imaging per protocol until progressive disease, death, initiation of a new anti-cancer therapy, or withdrawal of consent for study follow-up.*

12.0 TEST ARTICLE/STUDY DRUG

12.1 Blinded Investigational Product

CB-839 Tablets or Placebo Tablets

Test article (CB-839, 200 mg/tablet) or placebo tablets that are identical in appearance will be administered orally. CB-839 or placebo will be administered only to patients who have signed and dated an Informed Consent Form. Doses will be administered on Days 1 through 28 of each 28-day cycle. Dosing will not be adjusted for body weight or surface area.

The first CB-839 or placebo dose of the day will be administered in the morning immediately after breakfast. The evening/second dose should be taken immediately after a meal approximately 12 hr (\pm 2 hr) after the morning dose. CB-839 should be taken 2 hours before antacid therapy. See [Section 10.1.1](#) for discussion of acid suppression therapy.

Patients who vomit their CB-839 or placebo dose should be instructed NOT to make up that dose and to report the frequency of vomiting occurrences associated with study drug administration to the site.

Everolimus Tablets

Everolimus will be administered to patients who have signed and dated an Informed Consent Form. 10 mg everolimus will be administered on Days 1 through 28 of each 28-day cycle and should be taken orally QD around the same time every day. Administer either consistently with food or consistently without food. Everolimus dosing will not be adjusted for body weight or surface area.

12.2 Packaging and Labeling

CB-839 HCl Tablets (200 mg) are manufactured, packaged, and labeled according to current Good Manufacturing Practices (GMP). For additional information, please refer to the Pharmacy Manual.

Everolimus Tablets are available as 2.5, 5, or 10 mg strengths. Please refer to the everolimus Package Insert for specific instructions on packaging and labeling.

Placebo Tablets (200 mg equivalent) are manufactured, packaged, and labeled according to current GMP. For additional information, please refer to the Pharmacy Manual.

